Two copies of the Informed Consent form will be made. One copy remains in the patient's chart, another copy will be given to the patient, and the original will be filed with the case report form. The original consent will thus be available to the investigators, their staff, study monitors, and each institution's IRB.

5. Protection against Risks

All interviewers will undergo training by our consenting study coordinators and must demonstrate a high level of proficiency before being certified to interview subjects. Research fellows and study coordinators will be trained in all aspects of the study. Procedures used to assure the integrity of data include: (1) quarterly external audits by Outcomes Research staff, (2) data entry procedures following standard operating procedures (SOPs), and (3) data queries and resolution processes following SOPs. Frequent interaction among members of the study Executive Committee (PI, co-investigators, consultants), RAs, and others as necessary, will maintain overall quality assurance. They will meet or have conference calls at least quarterly throughout the data collection period, and as necessary thereafter.

The executive committee will evaluate all results from the proposed trial at least yearly, but more often if the Committee deems it necessary. It will be the responsibility of this committee to alert the IRB *via* letter to any untoward toxicity in one of the study groups. This committee, along with the IRB, will have exclusive authority to stop the study either because the hypotheses have been confirmed or denied, or because adverse events are detected. The executive committee will operate under guidelines published on the NCI web site.

6. Collaborating Sites

Single center

7. Gender and Minority Inclusion

We have no reason to believe that the effects of hemodynamic management on outcome are related to race or ethnicity. We will consequently include patients of all races and ethnicities and make a special effort to include minorities. We assume that our study population will reflect the patient population of each participating health system. In Cleveland, our participants will be roughly 10% Hispanic and 15% African American.

8. Inclusion of Children

Children will be excluded from the proposed studies.

REFERENCES

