Even when clinicians try to prevent intraoperative hypotension, they often fail because it is difficult to predict which patients will become hypotensive, much less when. A risk score for predicting minute-by-minute intraoperative hypotension is not currently available. Yet it seems likely that ability to identify when a patient is likely to become hypotensive, and the pathophysiology of the event, will improve hemodynamic management and perhaps patient outcome. Acumen HPI appears to be a reliable predictor of intraoperative hypotension, and should thus help clinicians anticipate and avoid hypotension. Furthermore, the secondary guidance provided by the Acumen HPI may help clinicians optimally manage fluids and thus prevent future episodes in the same patient.

AIMS

To determine whether use of Acumen HPI software to guide intraoperative hemodynamic management in the non-cardiac surgery reduces the duration and severity of hypotension.

PRIMARY HYPOTHESIS

Our primary hypothesis is that use of the Acumen HPI software guidance reduces TWA intraoperative hypotension below a threshold of 65 mmHg.

Specifically, we will compare the amount of intraoperative hypotension below mean-arterial pressure (MAP) threshold of 65 mmHg, in patients randomized to invasive arterial pressure monitoring vs. invasive arterial pressure monitoring with Acumen Hypotension Prediction Index software.

OUTCOMES

Primary:

1. Time- weighted average (TWA) MAP under a threshold of 65 mmHg.

Secondary:

- 1. Time-weighted average MAP below a threshold of 60 mmHg per case;
- 2. Time-weighted average MAP below a threshold of 55 mmHg per case.

Exploratory:

- 1. A composite of non-fatal cardiac arrest, in-hospital death, stroke, and MINS;
- 2. Acute kidney injury (AKIN criteria);
- 3. Quality of recovery (QoR-15) on postoperative day 3;
- 4. Postoperative morbidity survey (POMS) on postoperative day 3;
- 5. Transfusion requirement (ml packed red blood cells);
- 6. Amounts of intraoperative crystalloid and colloid;
- 7. Amount of vasoactive phenylephrine, ephedrine, nor-epinephrine, epinephrine, dobutamine;

- 8. Advanced hemodynamic variables- Cardiac output (CO), Cardiac Index (CI), Stroke Volume (SV), Stroke Volume Variation (SVV), Dynamic elastance (Edyn);
- 9. Hospital length of stay;
- 10. Hospital readmission within 30 days.

	Outcomes	Measurements			
1. Primary	TWA MAP drop under 65 mmHg threshold	Intraoperative record form EV1000 monitor			

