2. Secondary	TWA MAP drop under 60 mmHg threshold	Intraoperative record form EV1000 monitor			
	TWA MAP drop under 55 mmHg threshold	Intraoperative record form EV1000 monitor			
3. Exploratory	Composite of death, stroke, or MINS	From Cleveland Clinic Perioperative Health Documentation System PHDS and troponin first three postoperative mornings while in hospital from electronic health record (EHR)			
	Acute kidney injury	AKIN, creatinine			
	Quality of recovery (QoR-15):	POD 3, patient interview			
	Post-operative morbidity survey (POMS)	POD 3, EHR			
	Transfusion requirements (ml)	from PHDS			
	Amounts of intraoperative crystalloid and colloid (ml)	from PHDS			
	Amount of vasoactive – phenylephrine, ephedrine, nor-epinephrine, epinephrine, dobutamine (mg)	from PHDS			

Advanced hemodynamic	From EV100
variables	
Hospital length of stay	From PHDS
Hospital readmission within 30 days	From EHR

STUDY DESIGN

Experimental design

Single-center randomized comparison of invasive arterial pressure guided hypotension management vs. addition of Acumen HPI software guidance to the invasive arterial pressure monitoring on intraoperative hypotension duration and severity.

Subject selection

We will enroll ASA physical status 3-4 patients scheduled for moderate-to-high-risk surgery, who are ≥45 years of age. Potentially qualifying patients will be evaluated during their preoperative anesthesia clinic visits. We will enroll surgical patients meeting the following criteria:

Inclusion criteria

- 1. Written informed consent;
- 2. Age \geq 45 years;
- 3. ASA Physical Status 3 or 4;
- 4. Moderate- or high-risk surgery (for example, orthopedic, spine, urology, and general surgery);
- 5. Planned invasive blood pressure monitoring;
- 6. General anesthesia;
- 7. Surgery duration expected to last >2 hours;
- 8. Planned overnight hospitalization.

Exclusion criteria

- 1. Contraindication to the invasive blood pressure monitoring;
- 2. Pregnancy;
- 3. Emergency surgery;
- 4. Known clinically important intracardiac shunts;
- 5. Known a ortic stenosis with valve area ≤ 1.5 cm²
- 6. Known moderate to severe aortic regurgitation
- 7. Known moderate to severe mitral regurgitation
- 8. Known moderate to severe mitral stenosis

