Baseline Information: We will record demographic and morphometric characteristics include height (cm), weight (kg), age (yr.), sex, ASA physical status, and self-declared ethnicity. If available we will collect social history (tobacco and alcohol use), medical history (pulmonary disease, cardiovascular disease, neurologic disease, drug usage (including but not limited to: statins, β blockers, oral hypoglycemic agents and/or insulin), NSAIDs, diabetes (and whether insulindependent or not), and previous glucose-tolerance test results, preoperative hemoglobin and hematocrit, BUN and creatinine, electrolytes, preoperative EKG, and hemoglobin A₁c (HbA₁c). We will obtain contact information for each patient to facilitate follow-up.

Perioperative Data: Intraoperative care data will be accessed from electronic anesthesia information management system. The hemodynamic monitoring data will be downloaded from the monitors on to the secure Cleveland Clinic computers for analysis.

Anesthetic data will include the volatile anesthetic dose in MAC-hours, as well as total doses of propofol and other sedative hypnotics. Hemodynamic, respiratory parameters, BIS values and esophageal temperature will be recorded at regular intervals intraoperatively. Blood loss will be estimated; urine output and fluid administration including allergenic blood will be recorded. Intraoperative use and total dose of vasoactive drugs as well as antibiotic administration will be recorded. If available arterial blood gas results will be recorded.

Blood pressure measurements: A research fellow will be present in the operating room throughout the surgery. The research fellow will document when HPI alerts were generated and what is the probable cause based on the advanced hemodynamic parameters – hypovolemia, vasoplegia or decreased left ventricular contractility. The research fellow will also document the clinician's response; no action, fluid bolus, vasopressor started or increased, and inotrope started or increased. The hemodynamic monitoring data will be downloaded from the monitors on to the secure Cleveland Clinic computers for analysis.

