Length of stay: Length of stay (LOS) will be calculated end of surgery to time of discharge or death. We are considering Hospital LOS because not only it reflects morbidity, but also is important from hospital administration point of view, because hospitals want to utilize their resources in the most cost-effective way. According to Agency for Healthcare research and Quality average in 2010,

average hospital cost per stay was \$9,700, totaling \$375.9 billion.²² Furthermore, recent consideration of bundled payments by payers to reduce cost of healthcare while providing highest quality healthcare has provided increased impetus by the hospitals for reducing hospital LOS.

Table 2- Schedule of study events

Data	Screening Evaluation	Enrollment	Hemodynamic monitoring	Postoperative day three
Informed Consent	X			
Inclusion/Exclusion	X			
Criteria Evaluation				
Medical History		Х		
Demographic		X		
Vital Signs		X	X	
Surgery		X		
Information				
Monitoring			X	
duration				
Device memory			x	
data				
Adverse events			X	X
Hemodynamic			X	
management				
information				
Intraoperative			X	
medications				
Quality of recovery				X

Follow up

Patient will be followed up for major and minor complications as listed above. Patients will have a Troponin T drawn preoperatively and on the first and second days after surgery while patients remain hospitalized. Study personnel will recommend and attempt to obtain an ECG and/or

echocardiogram on patients with an elevated Troponin T. Patients will be queried about ischemic symptoms and pulmonary edema.

Research personnel will follow patients throughout their time in hospital evaluating the patients and reviewing their medical records ensuring trial orders are followed and noting any outcomes. If records/ patients indicate that they have experienced an outcome, study personnel will obtain the appropriate documentation.

PATIENT RECRUITMENT AND INFORMED CONSENT

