An initial training meeting before study enrollment will ensure reliability and consistency in the use of Acumen HPI software and written standard operating procedures (SOPs). At least 80% of the data will be independently audited to confirm consistency among patient records, study data sheets, and the main database. Data will be maintained on a custom-designed Access or SQL relational database. Data will be transcribed by separate sets of investigators. We have programmed and used similar password-protected databases in our previous major outcome trials. Trial management will be coordinated from the department of Outcomes Research, Cleveland.

HUMAN SUBJECTS RISKS AND PROTECTION

The Cleveland Clinic Institutional Review Board will approve the proposed trial. Written informed consent will be obtained from each participating patient. Patients who decline to participate will be given regional or general anesthesia and analgesia per their preference and that of their attending anesthesiologist; research data will not be collected from these patients.

1. Human Subjects Involvement and Characteristics:

The executive committee which will not otherwise be involved in day-to-day aspects of the protocol, will evaluate all results from the proposed trial. This committee, along with the IRB, will have exclusive authority to stop the studies either because the hypotheses have been confirmed, denied, or because adverse events are detected. It will be the responsibility of this committee to alert the IRB at each participating institution to any untoward toxicity in one of the study groups.

2. Sources of Material

Data obtained routinely for clinical purposes will be used in this study. Such data include: 1) anesthetic dose and safety monitoring; 2) fluid balance and transfusion requirements; 3) postoperative nausea and vomiting; 4) details of surgery; and 5) morphometric and demographic information. Postoperative outcomes will be retrieved daily from the patients' charts.

3. Potential risks to Subjects

Monitoring and Data Collection: Some data obtained routinely for clinical purposes will be used in this study. Such data include: anesthetic concentration and safety monitoring (end-tidal gases, arterial blood pressures, oxygen saturation, esophageal temperatures, intraoperative arterial blood gas samples, etc.), fluid balance, and urine volume. Recording these data is clinical standard and introduces no additional risk.

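### AKI is graded on creatinine, but no postoperative creatinine is scheduled and the baseline value is optional, so AKI can be classified only where routine care ordered the test

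*Combined protocol and SAP*

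**What the plan says.** - **Outcome.** AKI by AKIN criteria is exploratory outcome 2. The Outcomes table gives its measurement as "AKIN, creatinine", with no time points, window or data source. Neighbouring rows are fuller: the composite row names troponin on stated mornings, and QoR-15 and POMS are fixed to postoperative day 3.
- **Baseline value.** In Measurements, Baseline Information, the relevant sentence opens "If available we will collect social history" and runs on to "preoperative hemoglobin and hematocrit, BUN and creatinine, electrolytes". Preoperative creatinine falls under that condition.
- **Postoperative value.** Table 2 (schedule of study events) has no laboratory row. The Follow up section schedules one blood test: "Patients will have a Troponin T drawn preoperatively and on the first and second days after surgery while patients remain hospitalized".
- **Data source.** Sources of Material, under Human Subjects Risks and Protection, says "Data obtained routinely for clinical purposes will be used in this study" and has postoperative outcomes taken daily from the charts.
- **Blinding.** The Blinding section lists anesthesiologists, surgeons, data-gathering personnel and the operating room team as unblinded.
- **Analysis.** Data Analyses compares binary outcomes by Pearson chi-square or logistic regression. It has no rule for patients whose creatinine is missing.

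**The concern.** A creatinine-based diagnosis of acute injury compares a later value with an earlier one, so each patient needs both. The plan secures neither. Followed as written, it leaves the AKI denominator, and perhaps the numerator, to whoever happens to be tested in routine care.

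Two things are at stake. First, patients without a pair of values cannot be classified, whichever arm they are in. Second, testing could differ by arm. Surgeons and anesthesiologists know the allocation and how much hypotension occurred. The trial expects hypotension to differ by arm, and the Introduction links hypotension to kidney injury. The same two roles decide on ICU admission, which could affect how often blood is sampled.

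The protocol already recognizes this kind of problem for the heart. The Introduction says 93% of MINS goes unrecognized without troponin monitoring, and the Follow up section schedules troponin in all patients. AKI, also defined by a laboratory value, has no such protection.

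**Working it through.** The plan states no AKI rate, creatinine testing rate or AKI sample size, so there is no figure of its own to reproduce. The first check is of the text; the second is an illustration on assumed inputs.

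**Text check.** Creatinine appears in three relevant places: the AKI measurement entry, the conditional baseline list, and the POMS renal item in the Appendix. The POMS item also compares creatinine with the preoperative level. None of the three orders a draw. The only scheduled blood test is Troponin T, before surgery and on postoperative days 1 and 2 while in hospital.

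**Illustration.** Assumed: true AKI is 15% in both arms, so there is no real effect. From the Sample Size section: 107 patients per group. Let *t* be the proportion tested and *u* the AKI risk among untested patients.

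- Untested counted as AKI-free: observed AKI = 15% − (1 − *t*) × *u*
- Untested dropped: observed AKI = [15% − (1 − *t*) × *u*] / *t*

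| Tested, control vs HPI | *u* | Counted as AKI-free | Spurious relative reduction | Dropped |
|---|---|---|---|---|
| 95% vs 90% | 15% | 14.25% vs 13.5% | 1 − 0.90/0.95 = 5% | 15% vs 15% |
| 90% vs 80% | 15% | 13.5% vs 12.0% | 1 − 12.0/13.5 = 11% | 15% vs 15% |
| 90% vs 70% | 15% | 13.5% vs 10.5% | 1 − 0.70/0.90 = 22% | 15% vs 15% |
| 90% vs 80% | 5% | 14.5% vs 14.0% | 1 − 14.0/14.5 = 3% | 16.1% vs 17.5% |

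The last row makes untested patients lower risk, as one would expect if testing follows hypotension. Control: 15 − 0.10 × 5 = 14.5, and 14.5/0.90 = 16.1. HPI: 15 − 0.20 × 5 = 14.0, and 14.0/0.80 = 17.5. The same gap in testing then favours HPI slightly under one missing-data rule and disfavours it under the other.

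**Effect on the test.** With untested patients counted as AKI-free and *u* equal to the true rate, the exact rejection rate of the two-sided 5% chi-square test at 107 per group is:

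| True AKI, both arms | 90% vs 80% tested | 90% vs 70% tested |
|---|---|---|
| 5% | 4.6% | 5.7% |
| 10% | 6.1% | 8.6% |
| 15% | 6.4% | 10.6% |
| 20% | 6.8% | 12.6% |

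With equal testing in the two arms (100%, 90% or 70%) the rate stays between 4.3% and 5.3%, and the harm is lost events.

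**Patients lost.** At 10%, 20% or 30% untested, 107 × 0.10 = 10.7, 107 × 0.20 = 21.4 or 107 × 0.30 = 32.1 patients in an arm have no AKI classification.

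**The case against.** AKI is one of ten exploratory outcomes, with no hypothesis or sample size of its own. Using routine data from the chart is a deliberate, pragmatic choice. The Follow up section mentions trial orders that the document does not list, so a creatinine order may exist. All of this stands, and it limits the weight of the point. It does not supply a creatinine draw in the plan as written.

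Three stronger readings are tempting, and the documents support none of them.

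- **That unblinded clinicians decide who is found to have AKI.** The Blinding section covers anesthesiologists, surgeons, data-gathering personnel and the operating room team. It does not say whether ward or ICU clinicians, who may also order tests, know the arm. Nothing shows that ordering would differ by arm.
- **That the AKI result is biased toward HPI.** This requires less testing in the HPI arm and untested patients counted as AKI-free. The plan states no such rule. If those patients are dropped and are lower risk, the sign can reverse.
- **That the bias is about 11%.** This figure assumes 90% vs 80% testing and equal risk in tested and untested patients. The equal-risk assumption sits badly with the idea that testing follows hypotension. With 5% risk in the untested the figure is about 3%. Even the 1.5-point gap behind the 11% is small against its standard error: √[(0.135 × 0.865 + 0.12 × 0.88)/107] = 4.6 points.

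**Conclusion.** The point holds as a gap in measurement. The plan names AKI by creatinine as an outcome but secures neither of the two values needed, so classification depends on discretionary testing. Some patients may be unclassifiable, and the comparison is biased if testing differs by arm. Neither the direction nor the size of that bias can be derived from the documents. On assumed inputs it is roughly a 3% to 22% spurious relative reduction when untested patients count as AKI-free, and possibly a reversed sign when they are dropped. At 90% vs 80% tested the false-positive rate stays near nominal, so the harm there is mainly to the estimate, on which Data Analyses says the focus will fall along with its confidence interval.

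The time-weighted average MAP outcomes, primary and secondary, come from the EV1000 record and are untouched. This is a cheap improvement to an exploratory outcome, not a threat to the trial's main conclusion.

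**What to change.** 1. Reconcile the troponin days. The Outcomes table has troponin on the first three postoperative mornings; the Follow up section has days 1 and 2.
2. In the Follow up section and Table 2, add creatinine to the blood drawn for troponin, preoperatively and on the reconciled postoperative days, in both arms. If a creatinine order already exists among the trial orders, write it into the plan.
3. Base the main AKI analysis on the scheduled values and state the window. Report an analysis that adds clinician-ordered values as a sensitivity analysis.
4. Report by arm the number of patients without a creatinine pair, and state in advance how they are handled.

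The cost is one extra assay on existing samples and one row in Table 2, with no change to sample size. There are limits. Patients discharged early will still lack later values, since eligibility asks only for a planned overnight stay. Scheduled values alone miss AKI that appears after the last draw, which is why the sensitivity analysis is needed. If the reconciled days stop at day 2, the day-3 POMS renal item will still rely on routine creatinine.

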3.	The POMS (Grocott MP et al)	34
4.	Non-cardiac surgeries routinely requiring invasive monitoring:	35

TRIAL SUMMARY

Design: Single-center randomized comparison of invasive arterial pressure monitoring vs. arterial pressure monitoring combined with Acumen Hypotension Prediction Index (HPI) software guidance on intraoperative hypotension duration and severity.

Anticipated enrollment period: 12 months

Aim: To determine whether use of Acumen HPI software guidance to guide intraoperative hemodynamic management in the non-cardiac surgery reduces the duration and severity of hypotension.

Primary hypothesis: Our primary hypothesis is that adding Acumen HPI software guidance to the information provided by the invasive arterial pressure monitoring during moderate- to high-risk noncardiac surgery reduces time-weighted average (TWA) intraoperative hypotension below a threshold of 65 mmHg.

Outcomes:

Primary

1. Time-weighted average MAP below a threshold of 65 mmHg per case.

Secondary

- 1. Time-weighted average MAP below a threshold of 60 mmHg per case;
- 2. Time-weighted average MAP below a threshold of 55 mmHg per case.

Exploratory

- 1. A collapsed composite of non-fatal cardiac arrest, in-hospital death, stroke, and MINS;
- 2. Acute kidney injury (AKIN criteria);
- 3. Quality of recovery (QoR-15) on postoperative day 3;
- 4. Postoperative morbidity survey (POMS) on postoperative day 3;
- 5. Transfusion requirement (ml packed red blood cells);
- 6. Amounts of intraoperative crystalloid and colloid;
- 7. Amount of vasopressors phenylephrine, ephedrine, nor-epinephrine, epinephrine, dobutamine;
- 8. Advanced hemodynamic variables- Cardiac output (CO), Cardiac Index (CI), Stroke Volume (SV), Stroke Volume Variation (SVV);
- 9. Hospital length of stay;
- 10. Hospital readmission within 30 days.

Sample size: 213.

INTRODUCTION

In 2012, the global volume of surgery was estimated to be 312 million operations, a 33% increase from 2004.¹ According to Weiser et al, the increase in surgical volume is projected to grow with economic development. Surgery is associated with high mortality and morbidity, despite substantial improvements in technical expertise and patient monitoring. Overall inpatient 30-day mortality is about 2%, and climbs up to 6% in high-risk populations.²⁻⁷ More than 1% of patients aged 45 years or more die after major non-cardiac surgery while in the hospital or within 30 days of surgery.⁸

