To ensure efficient recruitment, research personnel will screen the patient list in the preoperative assessment clinic to identify eligible patients. Research personnel will use a variety of screening approaches to capture patients who do not attend the preoperative assessment clinic, including screening: the daily surgical list in the operating room, patients on surgical wards and intensive care units, and patients in the preoperative holding area. Center will also use all potential patient sources including asking the services of anesthesia, surgery, and medicine to page the study personnel regarding all surgical admissions through the emergency department and consultations for floor patients requiring surgery. Research personnel will approach all eligible patients to obtain informed consent. We will enroll patients undergoing surgery at single institution (Cleveland Clinic foundation, Cleveland, Ohio, USA)

DATA ANALYSES

Randomized groups will be compared on baseline variables using the standardized difference (difference in means or proportions divided by the pooled standard deviation), and such variables will be considered balanced if the absolute standardized difference is < 1.96 sqrt(2/N), where N is the per group sample size. Imbalanced variables will be adjusted for in all analyses.

The treatment effect of Acumen HPI guidance (versus no Acumen HPI guidance) on the primary outcome of intraoperative time- weighted average (TWA) MAP under a threshold of 65 mmHg will be assessed with a Wilcoxon-Mann-Whitney 2-sample 2-tailed test, or analogous test to account for imbalanced baseline variables or non-normal distribution of the outcome, as needed. Secondary and exploratory continuous outcomes will be analyzed in the same way.

Randomized groups will be compared on binary outcomes using a Pearson chi-square test or else logistic regression to adjust for baseline variables, as needed, and on oral outcomes using either the Wilcoxon Mann-Whitney test or a proportional odds logistic regression model, as appropriate.

For all analyses, focus will be on the estimated treatment effects and their confidence intervals, as well as the P-values. SAS statistical software, Carey, NC, will be used for all analyses.

SAMPLE SIZE CONSIDERATIONS

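### Length of stay ends at discharge or death, so under the planned rank test an early in-hospital death counts as a short, favourable stay

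*Combined protocol and SAP*

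**What the plan says.** Hospital length of stay is exploratory outcome 9. Under Measurements, the protocol closes the interval at either event: "Length of stay (LOS) will be calculated end of surgery to time of discharge or death". It gives two reasons for the outcome: "We are considering Hospital LOS because not only it reflects morbidity, but also is important from hospital administration point of view". The rest of that paragraph is about cost and resources.

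The Data Analyses section assigns the primary outcome a two-sided Wilcoxon-Mann-Whitney test, or an analogous test where needed, and adds: "Secondary and exploratory continuous outcomes will be analyzed in the same way". It also says: "For all analyses, focus will be on the estimated treatment effects and their confidence intervals, as well as the P-values".

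No section ranks in-hospital deaths as worst, censors them, restricts length of stay to survivors or plans a sensitivity analysis. Death is counted elsewhere among the outcomes, but within exploratory outcome 1: "A collapsed composite of non-fatal cardiac arrest, in-hospital death, stroke, and MINS".

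**The concern.** Put together, the definition and the test rank a death at the time it occurs. A patient who dies on day 1 ranks better than one discharged well on day 5. For bed occupancy this is correct, because the bed is free. For morbidity it runs the wrong way: the worst outcome scores as a good one.

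If one arm has more early deaths, its length of stay looks shorter and the other arm's looks relatively longer. Because the plan focuses on estimates and intervals, any such shift enters the reported result whether or not the test is significant. With death inside a collapsed composite, and no commitment to show deaths by arm alongside length of stay, a reader could not tell quicker recovery from earlier death.

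**Working it through.** **Inputs from the documents.** Total N is 213, about 107 per group, with alpha 0.05 (Sample Size Considerations). The planned figure reproduces closely. The usual Wilcoxon-Mann-Whitney formula with 80% power gives (1.960 + 0.842)² / (3 × 0.11²) ≈ 217 for a probability of 0.61, and 213 corresponds to 0.6108. That figure concerns the primary outcome; the plan gives no power or effect size for length of stay.

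**Assumed inputs.** The documents give no in-trial mortality or timing of death. The Introduction gives background rates only: "More than 1% of patients aged 45 years or more die after major non-cardiac surgery while in the hospital or within 30 days", about 2% overall, and up to 6% in high-risk populations. These bracket the values tried here but are not trial assumptions. They include 30-day deaths, and a death after discharge cannot shorten the stay. I label the arm with more deaths control and the other HPI; the result is symmetric.

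**Formula.** Let pC and pH be the in-hospital death proportions and u the share of survivors discharged before the deaths occur. Survivors have the same stay distribution in both arms. Counting ties as one half:

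P(HPI stay shorter) = 0.5(1−pC)(1−pH) + u·pC(1−pH) + (1−u)·pH(1−pC) + 0.5·pC·pH = 0.5 − (pC − pH)(0.5 − u)

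The null standard error with groups of 107 and 106 is √[(107+106+1)/(12×107×106)] = 0.0397. The chance of a nominal p<0.05 against the arm with fewer deaths is Φ(−1.96 + shift/0.0397), against 2.5% with no shift.

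| Deaths, control v HPI | 2% v 1% | 4% v 2% | 6% v 2% |
|---|---|---|---|
| Expected deaths, 107pC + 106pH | 3.2 | 6.4 | 8.5 |
| P, u = 0 (all deaths before all discharges) | 0.495 | 0.490 | 0.480 |
| Shift in null SE, u = 0 | 0.126 | 0.252 | 0.504 |
| Wrong-way chance, u = 0 | 3.3% | 4.4% | 7.3% |
| P, u = 0.25 | 0.4975 | 0.495 | 0.490 |
| Wrong-way chance, u = 0.25 | 2.9% | 3.3% | 4.4% |
| P, u = 0.5 | 0.500 | 0.500 | 0.500 |
| P, u = 1 (same as ranking deaths worst) | 0.505 | 0.510 | 0.520 |

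Simulation with 10,000 runs per case agrees: 2.9%, 4.3% and 7.3% at u = 0; 2.7%, 3.1% and 4.4% at u = 0.25; and 2.4% at u = 0.5 for 6% v 2%.

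The u = 0 rows are an upper bound. Inclusion asks only for "Planned overnight hospitalization", so some survivors may leave before the deaths.

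**Masking of a real benefit.** A second simulation (4,000 runs, 107 per arm) assumed lognormal stays with median 5 days and log SD 0.7, deaths at 0.2 to 2 days, and HPI survivor stays about 24% shorter. None of these values is in the documents. Power without deaths was about 78%.

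| Deaths, control v HPI | Deaths at time of death | Deaths ranked worst |
|---|---|---|
| 2% v 2% | 75% | 75% |
| 2% v 0% | 68% | 83% |
| 6% v 2% | 56% | 86% |

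**The case against.** The definition is explicit, and it fits most of its own rationale, since morbidity gets one clause and administration and cost get the rest. Morbidity and death are also measured more directly by exploratory outcomes 1 to 4. Each excess early death moves the probability by at most about 0.5/107 = 0.0047, or 0.12 standard errors. The 7.3% figure needs a threefold mortality difference with every death before every discharge, in a trial that excludes emergency and cardiovascular surgery and ejection fraction below 35%. Ranking deaths worst moves the result the same distance the other way, so it can show a benefit on length of stay when no survivor went home sooner.

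Much of this stands. The effect is small, the larger power losses rest on assumed inputs, and the current definition is right for resource use. Two parts do not remove the point. Outcome 1 reports death only as part of a collapsed composite, so it does not let a reader interpret length of stay. And for an outcome meant to reflect morbidity, a shift towards the arm with fewer deaths is the intended direction, whereas the present rule shifts away from it when deaths are early.

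**Conclusion.** The point holds as a minor one. Followed as written, the plan scores an early in-hospital death as a favourable stay, at odds with one of the two purposes it gives for the outcome. This reading of the text is secure; the size of the effect depends on assumed mortality and timing.

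Under those assumptions the shift is at most 0.005 to 0.020 in the Wilcoxon-Mann-Whitney probability, halves if a quarter of survivors leave before the deaths, and vanishes if half do. Equal mortality with equal timing gives no directional bias, and late deaths already rank as long stays. Only an exploratory outcome is affected; the primary and secondary outcomes and the sample size are not.

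**What to change.** For the between-group test, define length of stay as the time from end of surgery to discharge alive, and give in-hospital deaths the worst rank, longer than any observed stay. The planned rank test is kept. Report the number of in-hospital deaths by arm next to the result, and keep bed-days to discharge or death as a descriptive summary of resource use. Settle the rule before the data are analysed, so that it is not chosen after the deaths are known.

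The cost is one or two sentences in Data Analyses and one line of code. No new data are needed: in-hospital death is already collected for outcome 1, and the Sources of Material section says "Postoperative outcomes will be retrieved daily from the" charts. The downside is that the tested quantity becomes a ranking of stay or death and no longer bed-days, and death then counts in both outcome 1 and outcome 9. The report should say so.
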